9. SOFTWARE

SAS® Software Version 9.4. SAS Institute Inc., Cary, NC, USA.

10. SAP REVISION

Revision Date (DD MMM YYYY)	Section	Summary of Revision	Reason for Revision
24 JAN 2019	Section 2.2 and 2.3	Update analysis frequency	Administrative change
24 JAN 2019	Section 6.3.11	Update physical component score (PCS) to physical component summary (PCS), and mental component score (MCS) to mental component summary (MCS)	Administrative change
24 JAN 2019	Section 5.2	Update Oral systemic corticosteroids to Oral corticosteroids	Administrative change

11. APPENDIX

Appendix 1. Lists of RA Medications

1. List of of bDMARDs and Investigational bDMARDs (WHO Preferred Terms)

- ABATACEPT
- ADALIMUMAB
- ANAKINRA
- BAMINERCEPT
- BELIMUMAB
- BIMEKIZUMAB
- CABIRALIZUMAB
- CERTOLIZUMAB
- CERTOLIZUMAB PEGOL
- CLAZAKIZUMAB
- DENOSUMAB
- EPRATUZUMAB
- ETANERCEPT
- GOLIMUMAB
- INFLIXIMABINTERLEUKIN-2
- OCRELIZUMAB
- REMTOLUMAB
- RITUXIMAB
- SARILUMAB
- SECUKINUMAB
- SIRUKUMAB
- TABALUMAB
- TILDRAKIZUMAB
- TOCILIZUMAB
- TREGALIZUMAB
- Other investigational bDMARDs

2. List of Oral Corticosteroid (WHO Preferred Terms)

- BETAMETHASONE
- BETAMETHASONE DIPROPIONATE
- BETAMETHASONE SODIUM PHOSPHATE
- CORTISONE
- DEXAMETHASONE
- DEXAMETHASONE PALMITATE
- DEXAMETHASONE SODIUM PHOSPHATE
- MEPREDNISON
- METHYLPREDNISOLONE
- METHYLPREDNISOLONE ACETATE
- METHYLPREDNISOLONE SODIUM SUCCINATE
- MOMETASONE FUROATE
- PREDNISOLONE
- PREDNISOLONE FARNESYLATE
- PREDNISOLONE SODIUM SUCCINATE
- PREDNISON

3. List of Methotrexate (WHO Preferred Terms)

- METHOTREXATE
- METHOTREXATE SODIUM

Appendix 2. Health Assessment Questionnaire Disability Index (HAQ-DI)

The HAQ-DI score is defined as the average of the scores of eight functional categories (dressing and grooming, arising, eating, walking, hygiene, reach, grip, and other activities), usually administered by the patient. Responses in each functional category are collected as 0 (without any difficulty) to 3 (unable to do a task in that area), with or without aids or devices.

The highest score for questions in each category (range 0 to 3) determines the score for the category, unless aids or devices are required. Dependence on equipment or physical assistance increases a lower score (ie, scores of 0 or 1) to the level of 2 to more accurately represent underlying disability. The eight category scores are averaged into an overall HAQ-DI score on a scale from 0 (no disability) to 3 (completely disabled) when 6 or more categories are non-missing. If more than 2 categories are missing, the HAQ-DI score is set to missing. The HAQ-DI can be treated as a continuous measure.

The HAQ-DI score using aids (and/or devices) is computed by taking the maximum score of the questions in each category (range: [0, 3]) and whether or not aids/devices are used (0 or 1):

$$A = \begin{aligned} & \max(\text{dressing \& grooming category questions, 2*aids indicator}) + \\ & \max(\text{rising category questions, 2*aids indicator}) + \\ & \max(\text{eating category questions, 2*aids indicator}) + \\ & \max(\text{walking category questions, 2*aids indicator}) + \\ & \max(\text{hygiene category questions, 2*aids indicator}) + \\ & \max(\text{reach category questions, 2*aids indicator}) + \\ & \max(\text{grip category questions, 2*aids indicator}) + \\ & \max(\text{usual activities category questions, 2*aids indicator}) \end{aligned}$$

$$\text{HAQ-DI} = A / (\text{total number of categories with at least 6 non-missing})$$

The following table shows the contribution of the 43 questions used to calculate the HAQ-DI:

HAQ-DI Category:	Category questions: At least 6 categories must have scores to compute the HAQ-DI.		HAQ-DI Category Score with Aids/Devices Calculation:
	Category Questions	Aids/Devices Indicators	
Dressing/Grooming	HAQ0101, HAQ0102 (DRESS, HAIR)	HAQ0114, HAQ0119 (DRSG, GROOM)	
Using each question with a scale of 0-3, calculate the category score as the maximum of the category questions.
 
If the Aids/Devices indicator is “No”, no need to adjust the category score.
 
If the Aids/Devices indicator is “Yes” and the category score is <2, then the category score with the Aids/Devices is set to 2.
 
If the Aids/Devices indicator is “Yes” and the category score is ≥2, then the category score with Aids/Devices is the calculated category score without adjustment.
 
For example: The Dressing/Grooming category score is 2 if subject answered 1 for both questions 1 and 2 and “Yes” for both question 14 and 18.
 
In the HAQ-DI score calculation, questions on other device/aids will not be used.

Arising	HAQ0103, HAQ0104 (STAND, BED)	HAQ0116, HAQ0120 (CHAIR, ARISING)	
Eating	HAQ0105, HAQ0106, HAQ0107 (MEAT, LIFT, MILK)	HAQ0115, HAQ0121 (UTENSIL, EAT)	
Walking	HAQ0108, HAQ0109 (WALK, STEPS)	HAQ0110, HAQ0111, HAQ0112, HAQ0113, HAQ0122 (CANE, WALKER, CRUTCH, WHEEL, WALKING)	
Hygiene	HAQ0123, HAQ0124, HAQ0125 (WASH, BATH, TOILET)	HAQ0134, HAQ0135, HAQ0137, HAQ0139, HAQ0142 (RAISEAT, BATHBAR, BATHSEAT, LONGBATH, HYGIENE)	
Reach	HAQ0126, HAQ0127 (REACH, BEND)	HAQ0138, HAQ0143 (LONGRCH, REACH)	
Grip	HAQ0128, HAQ0129, HAQ0130 (OPENCAR, JAR, FAUCET)	HAQ0136, HAQ0144 (JAROPEN, GRIP)	
Activity	HAQ0131, HAQ0132, HAQ0133 (SHOP, INCAR, CHORES)	HAQ0145 (ERRAND)	

Handling Missing Data: If no more than 2 categories have missing category scores, then the HAQ-DI is the mean of the non-missing category scores. Otherwise, the HAQ-DI score is set to missing.

If any of the category questions are missing, but the aids/device indicator is non-missing, the category score can still be computed. However, if all category questions and its aids/device indicators are missing, then the category score is considered missing.

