13.5 Health Assessment Questionnaire - Disability Index (HAQ-DI)

HEALTH ASSESSMENT QUESTIONNAIRE

Name _____ Date _____

In this section we are interested in learning how your illness affects your ability to function in daily life.

Please tick the response which best describes your usual abilities OVER THE PAST WEEK:

	Without ANY Difficulty	With SOME Difficulty	With MUCH Difficulty	UNABLE To Do
DRESSING & GROOMING				
Are you able to:				
- Dress yourself, including tying shoelaces and doing up buttons?	_____	_____	_____	_____
- Wash your hair?	_____	_____	_____	_____
RISING				
Are you able to:				
- Stand up from a straight chair?	_____	_____	_____	_____
- Get in and out of bed?	_____	_____	_____	_____
EATING				
Are you able to:				
- Cut up your meat?	_____	_____	_____	_____
- Lift a full cup or glass to your mouth?	_____	_____	_____	_____
- Open a new milk carton?	_____	_____	_____	_____
WALKING				
Are you able to:				
- Walk outdoors on flat ground?	_____	_____	_____	_____
- Climb up five steps?	_____	_____	_____	_____

Please tick any of the following AIDS OR EQUIPMENT that you usually use for any of the activities mentioned above:

 Walking stick	 Aids used for dressing (button hook, zip-puller, long-handled shoe horn, etc.)
 Walking frame	 Specially adapted utensils (such as for eating and cooking)
 Crutches	 Specially adapted chair
 Wheelchair	 Other (Please specify: _____)

Please tick any of the following categories for which you usually need HELP FROM ANOTHER PERSON:

 Dressing and Grooming	 Eating
 Rising	 Walking

Please tick the response which best describes your usual abilities OVER THE PAST WEEK:

	Without ANY Difficulty	With SOME Difficulty	With MUCH Difficulty	UNABLE To Do
--	-------------------------------------	-----------------------------------	-----------------------------------	------------------------

HYGIENE

Are you able to:

- Wash and dry your body?
- Have a bath?
- Get on and off the toilet?

_____	_____	_____	_____
_____	_____	_____	_____

REACH

Are you able to:

- Reach up for and take down a 5 lb object (e.g. a bag of potatoes) from just above your head?
- Bend down to pick up clothing from the floor?

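### SAP Appendix 2 is inconsistent on a HAQ-DI category with no answered question and an aids/help indicator of 'No': the formula gives 0, the step table gives no score

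*SAP*

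**What the plan says.** SAP Appendix 2 describes the category score in three places.

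- **Formula.** Each of the eight categories contributes the maximum of its questions and twice its aids indicator; the eating term, for example, is "eating category questions, 2*aids indicator". The indicator records "whether or not aids/devices are used (0 or 1").
- **Step table.** The programmer is told to "calculate the category score as the maximum of the category questions". The score is left alone if the indicator is 'No' and raised to 2 if the indicator is 'Yes' and the score is below 2. Free-text aids are excluded: "In the HAQ-DI score calculation, questions on other device/aids will not be used".
- **Missing-data rules.** "If any of the category questions are missing, but the aids/device indicator is non-missing, the category score can still be computed". The next sentence is: "However, if all category questions and its aids/device indicators are missing, then the category score is considered missing".

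The safeguard on the total score is: "If more than 2 categories are missing, the HAQ-DI score is set to missing".

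On the questionnaire in Protocol Appendix 13.5, aids are recorded by ticking only: "Please tick any of the following AIDS OR EQUIPMENT that you usually use for any of the activities mentioned above". Help from another person is recorded in the same way. There is no 'No' box, yet the SAP codes the indicators Yes/No and 0/1. Neither document says whether an unticked box is stored as 'No' or as missing.

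**The concern.** A category that the patient skipped entirely carries no information on difficulty. If it enters the average as 0, it is scored as the best possible function and also helps to meet the six-category minimum. Two programmers could follow Appendix 2 faithfully, one using the formula and one the table, and obtain different HAQ-DI values from the same form.

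HAQ-DI is the measure of disability, which is part of a secondary objective. It is also one of the five ACR20/50/70 items (SAP 6.3.4, 6.3.5) and enters the ACR-N median (SAP 6.3.8). Where exactly two of the other four items have improved and both joint counts qualify, HAQ-DI decides the ACR20 result. A missing HAQ-DI would leave that result undetermined, whereas a spuriously improved one would make the subject a responder.

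**Working it through.** **The SAP's own example.** Dressing/Grooming, both questions answered 1, aids 'Yes'. Formula: max(1, 1, 2×1) = 2. Table: maximum 1, raised to 2. Both reproduce the stated 2.

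**No question answered.** The maximum is taken over non-missing arguments. The SAP does not say this, but a partly answered category could not otherwise be scored.

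| Indicator | Formula with missing-data rules | Step table |
|---|---|---|
| Missing | missing | missing |
| Yes (1) | 2 | 2, if an absent score is treated as below 2 |
| No (0) | 0, counted as scored | no maximum, nothing to adjust: no score |

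The last row is the inconsistency.

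**Size if the formula is programmed.** Take a subject with no real change, no aids or help ticked, a complete baseline with total category score T > 0, and k wholly blank post-baseline categories that truly sum to L.

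- HAQ-DI after baseline = (T − L)/8.
- Apparent improvement = [T/8 − (T − L)/8] / (T/8) = L/T.
- Each category is blank in k/8 of the possible placements, so the mean of L is kT/8 and the mean improvement is k/8: 1/8 = 12.5%, 2/8 = 25%, 3/8 = 37.5%. This holds for any profile.
- If blanks are treated as missing, HAQ-DI = (T − L)/(8 − k) for k ≤ 2. Its mean over placements is T/8, so the mean improvement is 0%. For k = 3 HAQ-DI is missing.

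**Illustration, all categories at 2.** Two blanks: 12/8 = 1.50 by the formula, against 12/6 = 2.00. Three blanks: 10/8 = 1.25, against missing.

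**Illustration, four categories at 2 and four at 1** (T = 12, HAQ-DI 1.50):

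| Blanks | L | Formula, L/12 | Blanks treated as missing |
|---|---|---|---|
| 1 | 1 to 2 | 8.3% to 16.7% | −4.8% to 4.8% |
| 2 | 2 to 4 | 16.7% to 33.3% | −11.1% to 11.1% |
| 3 | 3 to 6 | 25% to 50% | missing |

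In the same profile, blanks at core baseline work the other way. One blank in a category at 2 gives a baseline of 10/8 = 1.25 and a change of (1.25 − 1.50)/1.25 = −20%. Two give 8/8 = 1.00 and −50%.

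**Counter-case.** If the blank categories were truly 0, then L = 0 and the formula is right (0%). Averaging the answered categories then gives 1 − 8/7 = −14.3% for one blank and 1 − 8/6 = −33.3% for two.

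**Reach of the indicator.** The SAP table lists 2+2+2+5+5+2+2+1 = 21 indicators, at least one per category. The form has 7+6 listed aids and 4+4 help items, also 21, all tick-only. So if unticked is stored as 'No' and the formula is used, no category on a returned form could be missing and the safeguard on missing categories would never act. If unticked is stored as missing, a category with no answers and no ticks is missing under both rules.

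**The case against.** The best defence is that the text nowhere says a blank category scores 0. The final missing-data sentence gives a sufficient condition for missingness, not the only one. The sentence before it reads naturally as covering a partly answered category. The table points to no score. The rules also treat a missing indicator as a real state; the authors worked from the eCRF (SAP section 1), and that provision would have almost no use if every unticked box were stored as 'No'.

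Much of this stands. It shows that a score of 0 is one reading among two, and that the storage convention cannot be inferred from the paper form. It does not remove the inconsistency. Neither missing-data sentence requires an answered question, and the formula returns a number for exactly the case that the table leaves unscored. The no-imputation default in SAP 3.3.1 does not decide between them, because it gives way where a specific method is set out, as here.

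On size, the objection is also largely right. In the second illustration one blank stays below the ACR20 threshold, written queries on missing data (Protocol 8.10.3) will reduce blanks, and ACR response changes only when HAQ-DI is the deciding item.

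**Conclusion.** The point holds as an internal inconsistency of minor severity. The k/8 figures depend on the formula being the version programmed, on the maximum ignoring missing values, on 'No' being stored for a category with no answers, and on an otherwise unchanged subject with HAQ-DI above 0 and no aids. The apparent improvement is zero only where the blank categories were truly 0. None of the figures is a prevalence: the documents do not give the frequency of wholly blank categories.

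A reader might infer more: that the SAP scores every skipped category as no difficulty, that the six-category rule is a dead letter, and that reported HAQ-DI and ACR results will be inflated. The documents do not support that. The step table gives the opposite answer, the eCRF that would show how unticked boxes are stored is not supplied, and the primary objective is safety, with efficacy summarised descriptively and without testing (SAP 6.4). The effect on the secondary summaries is probably small.

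**What to change.** Replace the last sentence of Appendix 2 with: *A category score requires at least one answered category question; if no question in the category is answered, the category score is missing whatever the aids/device indicator. The at-least-6-categories rule is applied after this step, and this rule takes precedence over the formula.* The sentence before it can stay, since it then covers partly answered categories. Add one statement of how an unticked aids or help box is stored.

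The cost is two sentences of text and about one line of code. The analytical price is:

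- slightly more missing HAQ-DI and ACR-N values;
- some ACR20/50/70 results left undetermined, which become non-response under NRI (SAP 6.1);
- a blank category truly at 0 replaced in effect by the mean of the answered ones;
- a blank category with a reported aid no longer scored 2.

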Appendix 3. Corticosteroids

The following table will be used for converting non-prednisone medications to prednisone equivalent:

*Example: Subject is taking 8 mg of Methylprednisolone orally daily. To get the equivalent dose of prednisone: 8 mg Methylprednisolone = (5*8)/ 4 = 10 mg prednisone.*

Corticosteroids Name	Equivalent Dose (mg) to 5 mg Prednisone
Betamethasone	0.75
Betamethasone Dipropionate	0.75
Betamethasone Sodium Phosphate	0.75
Cortisone	20
Dexamethasone	0.75
Dexamethasone Palmitate	0.75
Dexamethasone Phosphate	0.75
Dexamethasone Sodium Phosphate	0.75
Hydrocortisone	20
Meprednisone	4
Methylprednisolone	4
Methylprednisolone Acetate	4
Methylprednisolone Sodium Succinate	4
Prednisone	5
Prednisolone	5
Prednisolone Farnesylate	5
Prednisolone Sodium Succinate	5
Triamcinolone	4
